3.4.3 Measures of Health System Benefit

- a) Time spent in the field by paramedics before arrival to hospital,
- b) Time spent in-hospital by paramedics before transfer of care to the ED team,
- c) ED length of stay until discharge or admission to hospital,
- d) Number of subsequent ED visits or admission to hospital within 30 days of ED discharge,

- e) Number of subsequent clinic/family physician visits within 30 days of ED discharge,
- f) Frequency of c-spine diagnostic imaging performed within 30 days of ED discharge, and
- g) Incremental cost per one immobilization avoided (including cost of training, equipment, paramedic time, ED utilization, diagnostic imaging, and follow-up visits).

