Primary outcome(s)	Proportion of patients immobilized Proportion of patients feeling comfortable (co-primary outcome)
Key secondary outcomes	Proportion of patients with a pain score ≤ 4/10 Time from EMS arrival to ED discharge or admission to hospital Patient radiation exposure from diagnostic imaging Number of skin pressure injuries Number of missed c-spine injuries Time spent in the field by paramedics before arrival to hospital Time spend in-hospital by paramedics before transfer of care

ED length of stay

Number of subsequent ED visits within 30 days

Number of subsequent clinical/family physician visits within 30 days

Frequency of c-spine diagnostic imaging performed within 30 days

Incremental cost per one immobilization avoided

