2.1 Background

Problem: Ontario Emergency Medical Services (EMS) annually transport half a million patients with a potential neck (cervical/c-spine) injury, from falls or motor vehicle collisions, to local emergency departments (ED). Ninety-five percent of those patients are alert and stable and at low risk of c-spine injury. Less than 1% actually have a c-spine fracture, and even less (0.5%) have a spinal cord injury. Spinal cord injuries result from moderate to severe blunt traumas and not from minor movements occurring during transport to hospital. Regardless, current EMS practice is to transport all such trauma victims (with or without c-spine injury) by ambulance using backboards, collars, and head immobilizers. These patients stay fully immobilized until an ED bed is made available, sometimes for as long as 3 hours. This prolonged immobilization is often unnecessary and increases patient discomfort, contributes to ED crowding, prolongs EMS intervention times, and adds a heavy financial burden to our healthcare system.

Why C-Spine Immobilization of Low-Risk Patients May Be Unwarranted: Not only is immobilization often unnecessary, its potential for clinical adverse effects and discomfort are well documented (3). Chest straps used in immobilization can have a pulmonary restrictive effect, even in healthy non-smokers. Immobilization on a board leads to progressively worse pain in the head, neck, and back area, often resulting in the necessity to perform diagnostic imaging on an otherwise normal spine in the ED. The presence of a c-spine immobilization collar has been associated with hyperextension, actually causing spinal cord injury in patients suffering from ankylosing spondylitis. In addition, c-spine collars can cause neck vein compression and increased intra-cranial pressure for patients with head injury, difficulty swallowing, and local skin necrosis.

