Once on an ED stretcher, it is not unusual for these patients to remain fully immobilized for several hours until physician assessment and c-spine diagnostic imaging can be performed and interpreted. This consumes valuable time for physicians, nurses, and radiology technicians and distracts them from other urgent responsibilities. These delays compound the burden of our crowded Canadian EDs in an era when they are under unprecedented pressures. The median length of stay for a patient evaluated in the stretcher area is approximately 8-12 hours, whereas similar minor trauma victims arriving without immobilization can be evaluated and discharged in less than 4 hours.

The Canadian C-Spine Rule: We have derived, validated, and implemented the Canadian C-Spine Rule (CCR) to be used by physicians (7-9), triage nurses (10), and paramedics (11) in more than 40,000 alert and stable trauma patients. The CCR (Figure 1) directs that immobilization is unnecessary if the patient has no high-risk criteria, has at least one low-risk criterion, and can voluntarily rotate their neck 45' left and right. Physicians and nurses already use the CCR in the ED to safely remove immobilization devices without the need for imaging and with no documented adverse outcomes. We recently completed a pilot implementation study with Ottawa paramedics where selective patients were transported without immobilization. We have recruited 3,854 patients, and paramedics have identified all clinically significant injuries (100% sensitivity) without negative consequence when the CCR determined that immobilization was not required (68% specificity). Approximately 60% of immobilizations were avoided.

[figure not shown]
C-Spine Evaluation in Children: The NEXUS decision instrument for use in adults and children was validated in 2,160 children aged 8 to 17 (12) and identified all significant injuries. The CCR's performance was superior to that of the NEXUS decision instrument when prospectively compared in an adult population (13), but has yet to be implemented for use in children. A case-control study of children younger than 16 with c-spine injuries identified 8 risk factors for significant injuries, 7 of which are included in the CCR (14).

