3.5 Participant Timeline

Patients with the potential for a c-spine injury will be enrolled in the study and evaluated with the CCR at the time of first contact with a paramedic. The paramedic documentation, as well as a completed study form will be reviewed by study staff to obtain the necessary information on the outcomes of interest. We will be partnering with the Institute for Clinical Evaluative Sciences (ICES) to obtain information on the initial ED visit, as well as any subsequent health care utilization within 30 days following the initial injury.

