5.1 Data Collection Methods

Once training of paramedic staff has been completed, paramedics will begin evaluating eligible patients with the CCR. Each time an eligible patient is assessed using the CCR, the paramedic treating that patient will complete and submit an electronic CCR (see Appendix 6. Paramedic Data Collection Form). The paramedic will also record patient-reported comfort level and pain level on this form. Staff at the study coordinating centre will receive the electronic EMS-completed CCR, as well as a copy of the Paramedic Care Record (ePCR). Study staff will review the paramedic documentation in order to assess compliance with the study protocol and application of the CCR. Information on patient age, gender, mechanism of injury, field time, offload time and immobilization status are contained in the ePCR and will be recorded from there (see Appendix 7. Study Data Collection Form).

We will link the information obtained from paramedic care records to provincial administrative databases housed at ICES. This linkage will allow us to obtain information related to the initial ED visit, c-spine diagnostic imaging, hospitalization, and subsequent ED/clinic/family physician visits within 30 days of injury.

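### As worded, the c-spine imaging outcome in Section 3.4.3(f) starts at ED discharge and so leaves out imaging done during the index ED visit

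*Combined protocol and SAP*

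**What the plan says.** Section 3.4.3 lists measures of health system benefit. Item (f) is "Frequency of c-spine diagnostic imaging performed within 30 days of ED discharge". Item (d), in the same list, is "Number of subsequent ED visits or admission to hospital within 30 days of ED discharge", and item (e) applies the same anchor to later clinic and family physician visits.

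Other sections describe the window differently:

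- Table 1 (Section 1.2) lists the outcome as "Frequency of c-spine diagnostic imaging performed within 30 days", with no start point.
- Section 3.5 says the linkage is "to obtain information on the initial ED visit, as well as any subsequent health care utilization within 30 days following the initial injury".
- Section 5.1 says "This linkage will allow us to obtain information related to the initial ED visit, c-spine diagnostic imaging, hospitalization, and subsequent ED/clinic/family physician visits", the last of these being limited to 30 days from injury.

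On where the imaging happens, Section 2.1 says that lying immobilized on a board causes worsening pain, "often resulting in the necessity to perform diagnostic imaging on an otherwise normal spine in the ED". It adds that patients may stay immobilized on an ED stretcher for hours "until physician assessment and c-spine diagnostic imaging can be performed and interpreted".

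**The concern.** The rationale and the outcome point at different parts of the patient's course. The Background describes imaging that takes place before the patient leaves the ED and presents it as a burden on ED and radiology staff. The outcome, listed as a health system benefit, begins counting once that visit is over. What it then measures is later imaging, such as deferred work-up. That could stay flat, or move in the opposite direction, while imaging in the index visit falls.

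There is also a pre-specification problem. With one window in Section 3.4.3, none in Table 1 and a broader description in Section 3.5, an analyst could defend either including or excluding the index visit. That choice should be fixed before the data are seen.

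**Working it through.** The plan gives no imaging rate, expected effect or power for this outcome, so there is no figure to reproduce. The check is a comparison of texts and of the order of events.

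**1. Order of events.** For each patient: injury, then index ED arrival, then imaging in the index visit (if any), then ED discharge.

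- Window in 3.4.3(f): from ED discharge to discharge + 30 days. Index imaging comes before the window opens, so it is out.
- Coverage described in Section 3.5: the initial ED visit, plus use up to injury + 30 days. Index imaging is in.
- Table 1: 30 days from an unstated point. Index imaging may be in or out.

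**2. Is the discharge reading the natural one?** Items (d) and (e) use the same phrase for events they call subsequent, so (f) reads as a post-discharge count too. Where the plan means index visit plus follow-up, it says so. Section 3.5 names both, and the costing text in Section 5.4 adds the 30 days after discharge to the health service costs. Item (f) has no such addition.

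**3. Does another outcome fill the gap?** Radiation exposure in 3.4.2(d) has no time window, and the cost measure in 3.4.3(g), with Section 5.4, includes ED use and diagnostic imaging. Both can reflect index imaging. Neither reports how often imaging was done.

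**4. Would a window from arrival need more data?** Arrival is no later than discharge, so arrival + 30 days ends no later than discharge + 30 days. Items (d), (e) and the cost follow-up already require data to discharge + 30 days. Sections 3.5 and 5.1 already request the initial ED visit, and Section 5.1 names c-spine imaging. No new data are needed.

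**5. Can the size be given?** Only by assumption. If a share p_index is imaged in the index visit and p_post after discharge, the outcome as worded captures p_post / (p_index + p_post) of all imaging:

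| p_index (assumed) | p_post (assumed) | Share captured |
|---|---|---|
| 0.60 | 0.03 | 0.03/0.63 = 4.8% |
| 0.80 | 0.03 | 0.03/0.83 = 3.6% |
| 0.60 | 0.10 | 0.10/0.70 = 14.3% |
| 0.80 | 0.10 | 0.10/0.90 = 11.1% |

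The result depends mainly on the post-discharge rate. Neither rate appears in the documents, so these rows illustrate direction and are not estimates.

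**The case against.** The strongest reply is that (f) may be a deliberate follow-up measure. It comes directly after two items on later health care use with the same anchor, and imaging after discharge is informative: if patients who were not imaged in the ED are imaged later, the trial should show it. That stands as a reason to keep the post-discharge count. It does not supply the missing index-visit count or explain why Table 1 gives no start point.

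A second reply is that index imaging is not lost to the trial, because it is linked and can show in radiation exposure and in costs. This is correct, and it limits what is at stake. The gap is in imaging frequency only.

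A third is that the conflict with Section 5.1 is looser than it looks. There, the phrase "subsequent ED/clinic/family physician visits within 30 days of injury" may limit only the visits and not the imaging. That also stands. The clearer mismatch is with Section 3.5.

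A reader might also infer that reducing ED imaging is a stated aim. The documents do not go that far. The link from immobilization to imaging is in the Background, while the Objectives (Section 2.2) name pain and discomfort, EMS times, ED length of stay and cost. Section 2.1 also says that ED physicians and nurses already use the rule to take patients out of immobilization without imaging, so how far index imaging would fall is uncertain.

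**Conclusion.** The point holds as a defect of definition in one secondary outcome. As worded, 3.4.3(f) excludes c-spine imaging in the index ED visit, no other outcome measures imaging frequency, and the start point is not settled across Section 3.4.3, Table 1 and Section 3.5. This rests on the plain reading of (f) and on index imaging preceding ED discharge. It needs no assumption about rates.

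The size cannot be computed from the documents. A reader might infer that the outcome would miss nearly all imaging, that the trial would show no imaging effect, or that it would show harm. Those conclusions need imaging rates and an effect size that the plan does not give, and they overlook the radiation and cost outcomes. The supportable statement is conditional: a change in index-visit imaging, if there is one, would not appear in this outcome. The co-primary outcomes and the sample size are unaffected.

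**What to change.** Redefine 3.4.3(f) as any c-spine imaging from index ED arrival through 30 days, and state the date from which the 30 days run. Report two components separately: imaging in the index visit and imaging after ED discharge. The second keeps the follow-up measure that may have been intended. Give the same start point for this outcome in Table 1.

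Leave the discharge anchor in 3.4.3(d), 3.4.3(e) and the cost follow-up. It suits events after the visit, and imposing a single day 0 on every outcome would change definitions in which this check found no error.

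The cost is more than an editorial correction. It means a logged revision under Section 1.3, Steering Committee and ethics board review under Section 7.2, and the registry update that Section 1.2 requires when Table 1 changes. The planned linkage already covers the initial ED visit and c-spine imaging, so no new data collection is needed.

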3.5 Participant Timeline

Patients with the potential for a c-spine injury will be enrolled in the study and evaluated with the CCR at the time of first contact with a paramedic. The paramedic documentation, as well as a completed study form will be reviewed by study staff to obtain the necessary information on the outcomes of interest. We will be partnering with the Institute for Clinical Evaluative Sciences (ICES) to obtain information on the initial ED visit, as well as any subsequent health care utilization within 30 days following the initial injury.

3.6 Sample Size

Our sample size for this study is determined mainly by pragmatic considerations: we need a large number of sites from across Ontario to evaluate safety and generalizability of implementation in this multicenter setting, while accounting for between-site differences such as size and setting. Power calculations were carried out for the stepped wedge trial. Using data from a previous study in these communities, we expect approximately 600 patients per EMS service per year (or 150 patients per 3 month time interval). A total of 12 EMS services (7,200 patients) evaluated across 4 time intervals in a stepped wedge design will provide at least 90% power to detect minimally important differences of 10% in our two co-primary outcomes using two-sided tests at the 2.5% level of significance. In particular, for our primary outcome we will have >99.9% power to detect a minimally important absolute reduction of 10% in the proportion of patients immobilized assuming a control arm proportion of 100%. For our co-primary outcome we will have 90% power to detect a minimally important increase of 10% in the proportion of patients feeling comfortable assuming a conservative control arm proportion of 50%. In these calculations, we have assumed a commonly used intracluster correlation coefficient (ICC) of 0.05, added 2 EMS services to account for variation in the number of patients across sites, and a further 2 EMS services to account for potential attrition.

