5.4 Statistical Methods

Analyses will be conducted at the level of individual patient data using generalized linear mixed effects regression with a random effect to account for clustering by EMS service, and fixed effects for treatment and time interval to account for the stepped wedge design. The primary and co-primary outcomes will be analyzed using binomial distribution with identity link and the effect of intervention will be expressed as absolute differences with 97.5% confidence intervals. Secondary outcomes will be similarly analyzed using binomial distribution and identity or logit link for dichotomous variables, normal distribution and identity link after log-transformation or gamma distribution and log-link for continuous variables with a skewed distribution, or Poisson or negative binomial distribution with log link for count variables. The effect of the intervention on each secondary outcome will be described using absolute difference, Relative Risk or Odds Ratio with 95% confidence interval. Subgroup analyses (described below) will be conducted by including interactions with time interval and treatment in the regression model.

Our **health economist** will perform a cost-effectiveness analysis from the perspective of the Ministry of Health and Long-Term Care. Trial data will be used to populate the relative costs and outcomes of the use of the CCR by paramedics with usual care (100% immobilization). Resource use will be collected during the trial and obtained from ICES, while unit costs will be obtained from appropriate Canadian

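### Replacing the fixed 2.5%/2.5% split with Holm's procedure would usually let comfort be tested at 5%, with overall error still at or below 5%: a free improvement, not a validity error

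*Combined protocol and SAP*

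**What the plan says.** Section 3.6 (Sample Size) plans "A total of 12 EMS services (7,200 patients) evaluated across 4 time intervals in a stepped wedge design", with "150 patients per 3 month time interval" in each service and an intracluster correlation of 0.05. It claims "at least 90% power to detect minimally important differences of 10% in our two co-primary outcomes", "using two-sided tests at the 2.5% level of significance". By outcome, the claims are:

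- Immobilization: ">99.9% power to detect a minimally important absolute reduction of 10% in the proportion of patients immobilized assuming a control arm proportion of 100" (per cent).
- Comfort: "90% power to detect a minimally important increase of 10% in the proportion of patients feeling comfortable assuming a conservative control arm proportion of 50" (per cent).

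For the primary and co-primary outcomes, section 5.4 (Statistical Methods) states that "the effect of intervention will be expressed as absolute differences with 97.5% confidence intervals". The analysis level therefore agrees with the design level.

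The documents give no testing order, Holm step, gatekeeping or other transfer of error rate between the two outcomes. They do not say whether the trial succeeds on one outcome or needs both. A 5% overall rate is not stated either; it is inferred from 2 × 2.5% and the 97.5% intervals. Section 6.2 plans no interim analyses, so nothing else draws on the error rate.

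**The concern.** The two outcomes are not equally uncertain. Section 3.3 has paramedics immobilize every eligible patient during usual care, so the control proportion is 100% by design. Section 2.1 reports that about 60% of immobilizations were avoided in the Ottawa pilot, against the 10 points used for power. Rejection for immobilization is close to certain, while comfort is the co-primary outcome whose result is in real doubt.

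Under a fixed split, the 2.5% assigned to immobilization is used once and then lost. Comfort is held to 2.5% even after immobilization has been shown, although a valid procedure at the same overall error rate would then allow 5%. What is at stake is some power on comfort; the soundness of the analysis is not in question.

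**Working it through.** **1. Inputs.** From section 3.6: two-sided level 0.025 per outcome; comfort 50% to 60% with 90% power; immobilization 100% to 90% with power above 99.9%; m = 150 per service and interval; T = 4 intervals; ICC 0.05; 12 services, of which 2 were added for unequal sizes and 2 for attrition. I read this as 8 services in the base calculation, which is an inference. From section 2.3: three steps.

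**2. Reproducing the stated comfort power.** The Hussey–Hughes variance is

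Var = Iσ²(σ² + Tτ²) / [(IU − W)σ² + (U² + ITU − TW − IV)τ²].

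Here σ² = 0.25/150 = 0.001667 and τ² = 0.25 × 0.05/0.95 = 0.01316, taking p(1 − p) at 50% as the within-service variance.

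- *8 services (3, 3 and 2 per step).* U = 17, W = 109, V = 41, so the bracket is 27σ² + 69τ² = 0.9529. The numerator is 8 × 0.001667 × 0.05430 = 0.000724. SE = √0.000760 = 0.0276. Power at 2.5% = Φ(0.10/0.0276 − 2.241) = 91.7%.
- Other variance conventions with 8 services give 92.0% to 93.6%; a t-based version with 20 degrees of freedom gives 89.6%. The stated 90% is consistent with these.
- *12 services (4 per step).* U = 24, W = 224, V = 56, so the bracket is 64σ² + 160τ² = 2.212. The numerator is 0.001086. SE = 0.0222. Power at 2.5% = 98.8% (98.8% to 99.3% across conventions).

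Immobilization power exceeds 99.99% in every variant with 8, 10 or 12 services, in line with the stated figure.

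**3. Comfort at 5% once immobilization is rejected.**

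- From the stated 90%: 2.241 + 1.282 = 3.523, and Φ(3.523 − 1.960) = 94.1%. Type II error falls from 10% to 5.9%.
- Averaging over immobilization at 99.9% power, Holm gives 0.999 × 0.941 + 0.001 × 0.90 = 94.1%.
- The information needed for 90% power falls to (1.960 + 1.282)²/(2.241 + 1.282)² = 0.847 of what it was, about 15% less.

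| Setting | Comfort at 2.5% | Comfort at 5% |
|---|---|---|
| Stated power | 90% | 94.1% |
| 8 services, constant ICC | 91.7% | 95.2% |
| 12 services, constant ICC | 98.8% | 99.5% |
| 12 services, correlation decaying (cluster autocorrelation 0.9, assumed) | 89.7% | 93.9% |
| 12 services, correlation decaying (cluster autocorrelation 0.8, assumed) | 76.1% | 83.9% |

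The last two rows use an assumption that is not in the documents.

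**4. Overall error.** Simulation with both nulls true, at test correlations 0, 0.3 and 0.6, gives 4.96%, 4.86% and 4.47% for Holm. These equal the fixed split, because Holm makes a first rejection only when the split does. If immobilization truly changes and comfort does not, the only possible false claim is comfort, tested at no more than 5%. Testing comfort at 5% unconditionally, with immobilization at 2.5%, would give 1 − 0.975 × 0.95 = 7.4% for independent tests (bound 7.5%).

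**5. Intervals.** Width ratio 1.960/2.241 = 0.874, so a 95% interval is about 13% narrower than a 97.5% interval. Two 97.5% intervals have joint coverage of at least 1 − 2 × 0.025 = 95%. Two 95% intervals guarantee only 90% (0.95² = 90.25% if independent).

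**The case against.** The strongest reply is that nothing is broken. An equal split is a standard, conservative rule; sections 3.6 and 5.4 apply it consistently; and comfort reaches the plan's own 90% target at 2.5%. That stands, and it is why this is an improvement rather than a correction.

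The reply also limits the size. The four services added as allowances may all contribute, and power at 2.5% is then already about 99%. Section 3.6 says the sample size is mainly pragmatic and section 3.7 expects 8,129 eligible cases against 7,200 required, so the 15% saving in information would change no planning decision. On the other side, section 5.2 says missed cases will not be followed up, so the information obtained may fall short.

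Three stronger readings are tempting and should be resisted.

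- A reader might infer that comfort can simply be tested at 5%. It can be only after immobilization is rejected, or if both outcomes must succeed.
- A reader might infer that the narrower comfort interval comes free. Holm protects the tests; it does not make two marginal 95% intervals jointly 95%.
- A reader might infer that a fixed sequence, immobilization first, risks less than 0.1%. That figure is power assuming the planned test works. Section 5.4 uses a binomial identity-link mixed model, and with control values at 100% it may fail to fit. Under a fixed sequence, that failure would block the comfort claim. The current split does not carry this risk, and neither does Holm.

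**Conclusion.** The point holds as a free improvement in testing, not as an error in validity. For hypothesis tests Holm is never worse than the planned split: it rejects everything the split rejects, sometimes more, and keeps overall error at or below 5%. Comfort's own false-positive rate can rise from 2.5% to 5% once immobilization is rejected; that is the released error rate being used within the same total.

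The gain in comfort power is about 4 points from the stated 90%, and under 1 point if all 12 services contribute fully with a constant ICC of 0.05. It would be larger if within-service correlation decays over time, on which the documents are silent.

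The conclusion rests on two inferences: that 2.5% per outcome is a split of an overall 5%, and that success on either outcome counts. If both must succeed, the split is unnecessary for a different reason, and each outcome can be tested at 5% without Holm.

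**What to change.** In section 3.6, state whether success requires one co-primary outcome or both.

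- **If either suffices,** replace the fixed split in sections 3.6 and 5.4 with Holm: test the smaller of the two p-values at two-sided 2.5% and, if it is rejected, test the other outcome at two-sided 5%. Add that if the immobilization model yields no usable p-value, that outcome counts as not rejected and comfort is tested at 2.5%, as now.
- **If both are required,** test each at two-sided 5% and drop the split.

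Keep the 97.5% intervals where joint 95% coverage is wanted. If a 95% interval for comfort is also reported, label it marginal. A fixed sequence with immobilization first is possible but less safe, because of the fitting risk at 100%.

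The cost is a few sentences, with no added patients, sites or data. The wording should be settled before outcome data are seen, by the amendment route in section 7.2.
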